**6.4. Changes From Protocol-Specified Efficacy Analyses**

One of the secondary objectives of this study for Groups 1-3 and 5:

To characterize steady-state pharmacokinetics (PK) of study drugs

GS-9992 drug development was stopped by Spring Banks and the study team decided not to perform PK analysis and the collected PK samples will be stored.

## **7. SAFETY ANALYSES**

### **7.1. Adverse Events and Deaths**

#### **7.1.1. Adverse Event Dictionary**

Clinical and laboratory adverse events (AEs) will be coded using the current version of MedDRA. System organ class (SOC), high level group term (HLGT), high level term (HLT), preferred term (PT), and lower level term (LLT) will be provided in the AE dataset.

#### **7.1.2. Adverse Event Severity**

Adverse events are graded by the investigator as Grade 1, 2, 3, or 4 according to toxicity criteria specified in the protocol. The severity grade of events for which the investigator did not record severity will be categorized as “missing” for tabular summaries and data listings. The missing category will be listed last in summary presentation.

Severity of adverse events will be determined by the investigator as mild, moderate, or severe. The severity of events for which the investigator did not record severity will be categorized as “missing” for tabular summaries and data listings. The missing category will be listed last in summary presentation.

#### **7.1.3. Relationship of Adverse Events to Study Drug**

Related AEs are those for which the investigator selected “Related” on the AE eCRF to the question of “Related to Study Treatment.” Relatedness will always default to the investigator’s choice, not that of the medical monitor. Events for which the investigator did not record relationship to study drug will be considered related to study drug for summary purposes. However, by-subject data listings will show the relationship as missing.

#### **7.1.4. Serious Adverse Events**

Serious adverse events (SAEs) will be identified and captured as SAEs if AEs met the definitions of SAEs that were specified in the study protocol. SAEs captured and stored in the clinical database will be reconciled with the SAE database from the Gilead Global Product Safety (GLPS) before database finalization.

## 7.1.5. Treatment-Emergent Adverse Events

### 7.1.5.1. Definition of Treatment-Emergent Adverse Events

For the **Analysis for 12 Week Regimen**, treatment-emergent adverse events (TEAEs) are defined as follows:

- For subjects treated with GS-9992 and TAF or commercially available NUC(s) (ie, Group 1, 3, 4 and 5):

Any AEs with an onset date on or after the first dose date of any study drug and no later than 30 days after permanent discontinuation of GS-9992

Any AEs leading to premature discontinuation of any study drug during the first 12 weeks (ie, from Day 1 to Day 84).

- For subjects treated with TAF only (ie, Group 2):

For those who remained on TAF treatment for the first 12 weeks plus 30 days (ie, from Day 1 to Day 114):

- Any AEs with an onset date on or after the first dose of TAF and no later than 30 days after the first 12 weeks treatment of TAF (ie, no later than Day 114)

For those who prematurely discontinued TAF during the first 12 weeks plus 30 days (ie, from Day 1 to Day 114):

- Any AEs with an onset date on or after the first dose of TAF and no later than 3 days after permanent discontinuation of TAF or up to Day 114, whichever comes earlier
- Any AEs leading to premature discontinuation of TAF

For the **Analysis for 48 Week Regimen**, TEAEs are defined as follows:

- For subjects treated with GS-9992 and TAF (ie, Group 1, 3 and 5):

Any AEs with an onset date on or after the first dose date of any study drug and no later than 3 days after permanent discontinuation of TAF or 30 days after permanent discontinuation of GS-9992, whichever comes last

Any AEs leading to premature discontinuation of any study drug during the 48 weeks treatment

- For subjects treated with TAF only (ie, Group 2):

Any AEs with an onset date on or after the first dose date of TAF and no later than 3 days after permanent discontinuation of TAF

Any AEs leading to premature discontinuation of TAF during the 48 weeks treatment

- Subjects treated with GS-9992 and commercially available NUC(s) (ie, Group 4) are not included in treatment-emergent **Analysis for 48 Week Regimen**.

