**6.5. 24-Week Treatment Free Assessments ( Weeks 4, 8, 12, 16, 20, and 24, All Visits Have Window of  $\pm$  5 Days)**

Subjects that meet the criteria for the treatment free follow-up (Section 3.2) will be followed for 24 weeks or until the initiation of alternative CHB therapy, whichever comes first.

The following assessments will be completed:

- Complete Physical examination at Week 4
- Symptom-directed physical examination
- Review adverse events at Week 4 and collect SAEs through the end of study
- Review concomitant medications
- Vital signs
- Sample collection for:
  - Safety laboratory tests (hematology and chemistry)
  - Quantitative plasma HBV DNA
  - Quantitative serum HBsAg, CCI
  - Qualitative HBV serology (HBeAg [reflex HBeAb if HBeAg is negative] and HBsAg [reflex HBsAb if HBsAg is negative]) to be collected at Weeks 12 and 24

- Collection of PBMC, whole blood, serum, and plasma samples for biomarker analysis at Weeks 4, 8, 12, and 24 (PBMC sample collection is only required at the sites that have access to PBMC processing laboratory).
- Serum sample for HBV viral sequencing (resistance surveillance) or ddPCR (Group 4)
- Urine pregnancy test (females of child bearing potential only at Week 4)

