#### **6.6. Assessments for Early Discontinuation from the Study**

If a subject discontinues study dosing (for example, as a result of an AE), every attempt should be made to keep the subject in the study and continue to perform the required study-related follow-up and procedures (see Section 6.5 Post-Treatment Assessments).

If this is not possible or acceptable to the subject or investigator, the subject may be withdrawn from the study.

Criteria for study treatment discontinuation and Toxicity Management can be found in Section 6.11 and Section 7.6.

The Early Discontinuation (ED) Visit should be performed within 14 days from notification of study discontinuation. The following assessments will be performed at the ED visit:

- Vital signs
- Review AEs and concomitant medications
- Complete Physical Examination
- Body Weight
- 12-lead ECG (Subjects must rest quietly in the supine position for a minimum of 5 minutes prior to the recording)
- Sample collection for:
  - Safety Laboratory Tests (hematology, chemistry, and urinalysis)
  - Quantitative plasma HBV DNA
  - Quantitative serum HBsAg, CCI
  - Qualitative HBV serology (HBeAg [reflex HBeAb if HBeAg is negative] and HBsAg [reflex HBsAb if HBsAg is negative])
  - Estimated creatinine clearance (using the Cockcroft-Gault method)

- Serum sample for HBV viral sequencing (resistance surveillance) or ddPCR (Group 4)
  - Single Plasma PK sample
  - Urine pregnancy test (females of child bearing potential only)
  - Collection of PBMC, whole blood, serum, and plasma samples for biomarker analysis (PBMC sample collection is only required at the sites that have access to PBMC processing laboratory).
- GS-9992 and TAF accountability, as applicable

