#### **Adverse Events**

Following initiation of study medication, collect all AEs, regardless of cause or relationship, until 30 days after last administration of study IMP must be reported to the eCRF database as instructed.

All AEs should be followed up until resolution or until the adverse event is stable, if possible. Gilead Sciences may request that certain AEs be followed beyond the protocol defined follow up period.

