#### **2.1.1. Analysis for 12 Week Regimen**

The Analysis for 12 Week Regimen will include data collected through 30 days after the last dose of GS-9992 (Groups 1, 3-5) or 30 days after 12 weeks treatment of TAF (Group 2).

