#### For the **Analysis for 12 Week Regimen**:

- For subjects treated with GS-9992 and TAF or commercially available NUC(s) (ie, Group 1, 3 -5):

30 days after permanent discontinuation of GS-9992

- For subjects treated with TAF only (ie, Group 2):

For those who remained on TAF treatment for the first 12 weeks plus 30 days (ie, from Day 1 to Day 114):

- 30 days after the first 12 weeks treatment of TAF (ie, no later than Day 114)

For those who prematurely discontinued TAF during the first 12 weeks plus 30 days (ie, from Day 1 to Day 114):

- 3 days after permanent discontinuation of TAF or up to Day 114, whichever comes earlier

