#### For the **Analysis for 48 Week Regimen**:

- For subjects treated with GS-9992 and TAF (ie, Group 1, 3 and 5):

3 days after permanent discontinuation of TAF or 30 days after permanent discontinuation of GS-9992, whichever comes last

- For subjects treated with TAF only (ie, Group 2):

3 days after permanent discontinuation of TAF

- Subjects treated with GS-9992 and commercially available NUC(s) (ie, Group 4) are not included in treatment-emergent **Analysis for 48 Week Regimen**.

If the relevant baseline laboratory value is missing, any abnormality of at least Grade 1 observed within the time frame specified above will be considered treatment-emergent.

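### For subjects who stop all study drug before Day 111, the safety tables follow the GS-9992 groups up to 27 days longer than the TAF control

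*SAP*

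**What the plan says.** **12-week tables.** For the groups that receive GS-9992, SAP 7.1.5.1 counts AEs with onset "no later than 30 days after permanent discontinuation of GS-9992". A Group 2 subject who stays on TAF is counted to Day 114. One who stops TAF before then is counted "no later than 3 days after permanent discontinuation of TAF or up to Day 114, whichever comes earlier".

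**48-week tables.** Groups 1, 3 and 5 are counted to "3 days after permanent discontinuation of TAF or 30 days after permanent discontinuation of GS-9992, whichever comes last". Group 2 is counted to TAF stop + 3 days. Group 4 is not in these tables.

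**Laboratory abnormalities.** SAP 7.2.3.1 uses the same cutoffs for both sets of tables.

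**Exception.** In every group, AEs that lead to premature discontinuation of study drug are counted through a separate clause. Laboratory abnormalities have no such clause.

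**Related text.** SAP 2.1.1 puts the data scope of the 12-week analysis at 30 days beyond the 12 weeks for Group 2, as for the other groups after GS-9992. SAP 3.8.2 treats data up to 3 days after the last dose as on-treatment in Groups 1, 2, 3 and 5. For AEs after the start of study medication, Protocol 7.3 requires that those of any cause "until 30 days after last administration of study IMP must be reported", with no distinction by group.

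**The concern.** Safety and tolerability of the 12-week regimens is a primary objective. The incidence tables are presented by treatment group, and Group 2 is the only control.

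If a Group 1 subject and a Group 2 subject both stop everything on Day 29 and both have a new Grade 3 laboratory value on Day 45, the value is treatment-emergent in Group 1 and not in Group 2. The difference comes from the counting rule and not from the drugs.

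For subjects who stay on treatment, the SAP sets the same Day 114 cutoff in Group 2 as in the GS-9992 groups. Only early stoppers lose that match, and the SAP gives no reason.

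**Working it through.** **The plan's own figure.** Twelve weeks plus 30 days is 12 × 7 + 30 = 84 + 30 = Day 114, as SAP 7.1.5.1 states.

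**Cutoffs.** Let T be the day on which all study drug has stopped. GS-9992 then stopped on min(T, 84).

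- 12-week, Groups 1, 3, 5: min(T, 84) + 30
- 12-week, Group 2: min(T + 3, 114) for an early stop, otherwise 114
- 48-week, Groups 1, 3, 5: max(T + 3, min(T, 84) + 30)
- 48-week, Group 2: T + 3

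| Stop day T | 12-week: Groups 1, 3, 5 v Group 2 | 48-week: Groups 1, 3, 5 v Group 2 | Gap (days) |
|---|---|---|---|
| 14 | 44 v 17 | 44 v 17 | 27 |
| 29 | 59 v 32 | 59 v 32 | 27 |
| 84 | 114 v 87 | 114 v 87 | 27 |
| 90 | 114 v 93 | 114 v 93 | 21 |
| 110 | 114 v 113 | 114 v 113 | 1 |
| 111 | 114 v 114 | 114 v 114 | 0 |
| 168 | 114 v 114 | 171 v 171 | 0 |

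In both sets of tables the gap is 27 days for T up to 84, 111 − T for T from 85 to 110, and 0 from Day 111.

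**Can data fall in the gap?**

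- AEs: yes, by the collection rule in Protocol 7.3.
- Early Discontinuation visit, which includes safety laboratory tests (Protocol 6.6): "The Early Discontinuation (ED) Visit should be performed within 14 days from notification of study discontinuation". Assuming notification on the stop day, the visit falls on stop + 0 to + 14. All 15 of those days are within + 30, and 4 of 15 are within + 3.
- Treatment-free Week 4 visit, with laboratory tests (Protocol 6.5, ± 5 days). With the SAP Table 3-5 nominal FU Day 29, the allowed days are 24 to 34: 7 of 11 are within + 30 and none within + 3. If the end of Week 4 is taken as 28 days, the allowed days are 23 to 33: 8 of 11 and none.

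**How many control subjects?** The documents give no expected rate for Group 2, so I assume the TAF Phase 3 rate. Protocol Table 1-2 lists TAF subjects without Week 48 virologic data because they discontinued: (0 + 3 + 6) + (1 + 6 + 19) = 35 of 285 + 581 = 866, or 4.04%.

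- Stops spread evenly over 336 days: 4.04% × 110/336 = 1.32%. Expected number is 10 × 0.0132 = 0.13; chance of at least one is 1 − (1 − 0.0132)^10 = 12%.
- All stops by Day 110: expected number is 10 × 0.0404 = 0.40; chance of at least one is 1 − (1 − 0.0404)^10 = 34%.

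If every one of these subjects had an event in the gap and none counted otherwise, the expected understatement in Group 2 would be 0.13/10 to 0.40/10, that is 1.3 to 4.0 points. A single subject moves Group 2 by 1/10 = 10 points and a group of 30 by 1/30 = 3.3 points. The documents give no discontinuation rate for GS-9992 plus TAF, so I put no figure on that side.

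**The case against.** **The lag follows the drug, not the arm.** In the 48-week tables every subject in Groups 1, 2, 3 and 5 gets TAF stop + 3 days, and the GS-9992 lag is added only where GS-9992 was taken. The 3 days match the on-treatment convention of SAP 3.8.2. This explains the rule. It does not make the comparison equal: a Group 1 subject who stops both drugs on Day 29 is also off TAF, yet is counted to Day 59.

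**A reader might infer that the SAP contradicts the protocol.** It does not. Protocol 7.3 governs collection, not tabulation. Protocol 8.6 ties the primary safety window to the last dose of GS-9992, which Group 2 never takes, and Protocol 8.6.2 defines no treatment-emergent window. For the same reason, the shorter count for someone who stops GS-9992 alone and continues TAF follows the protocol's window and is not an error.

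**A reader might infer that the omitted control events disappear.** They do not. All AEs are listed. Some later laboratory values can reach the treatment-free follow-up (TFFU) summaries in SAP 7.2.2, 7.2.3.2 and 7.2.4, which carry no Week 48 limit. That route is partial. TFFU abnormalities are graded against the last on-treatment value, so they are not the same measure. A subject seen only at an Early Discontinuation visit does not enter TFFU. The TFFU sets in SAP 7.1.6 (AEs) and 7.2.3.3 (laboratory) are worded as after Week 48, whereas TFFU after a Day 29 stop ends about Day 29 + 168 = Day 197.

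**The effect is small.** AEs leading to discontinuation already count in every group. A subject with an earlier treatment-emergent AE adds nothing to the any-AE row. The direction inflates GS-9992 relative to control, so the rule cannot hide harm from GS-9992. All of this stands and limits the weight of the point.

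**Conclusion.** The point holds as a limited one. For subjects who stop all study drug before Day 111, the treatment-emergent cutoffs are unequal between Groups 1, 3 and 5 and the TAF control: by 27 days for stops up to Day 84, then by 26 falling to 1 day. For stops from Day 111 to the end of the 48 weeks they are equal, so it would be wrong to read the 48-week tables as unequal throughout.

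The day counts follow from the SAP text and assume only that GS-9992 ends by Day 84 and that both drugs stop together before then. The number affected is an assumption: about 0.1 to 0.4 of 10 control subjects, with a 12% to 34% chance of at least one, if the TAF Phase 3 rate carries over.

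The tables are descriptive, and Groups 3 and 5 are not randomised against Group 2. Correction is optional, but worth making because it is cheap and one subject is 10 points in the control.

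**What to change.** Change the Group 2 cutoffs only, in SAP 7.1.5.1 and 7.2.3.1:

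- 12-week tables, early stoppers: TAF stop + 30 days, capped at Day 114, i.e. min(T + 30, 114).
- 48-week tables: the later of TAF stop + 3 days and 30 days after the earlier of TAF stop and Day 84, i.e. max(T + 3, min(T, 84) + 30).

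For a Day 29 stop both give Day 59, as in the GS-9992 groups. For a Day 90 stop both give Day 114. For a Day 168 stop the 12-week cutoff is Day 114 and the 48-week cutoff is Day 171. The gap is 0 for every common stop day from 1 to 336, and the GS-9992-based window of Protocol 8.6 is untouched. A 3-day lag in all groups would also be equal, but would leave out events that the Protocol 8.6 window includes.

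Record the change in the SAP revision table (Section 11).

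The cost is wording in two sections and one derivation for Group 2. No new data are needed: AEs are already collected for 30 days and the laboratory visits are already scheduled. Some laboratory values will not exist, because subjects in treatment-free follow-up "will be followed for 24 weeks or until the initiation of alternative CHB therapy, whichever comes first". The downside is that a few off-treatment events are added to Group 2.

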#### 7.1.5.2. Incomplete Dates

If the onset date of the AE is incomplete and the AE stop date is not prior to the first dosing date of study drug, then the month and year (or year alone if month is not recorded) of onset determine whether an AE is treatment emergent. The event is considered treatment emergent if both of the following 2 criteria are met:

- The AE onset is the same as or after the month and year (or year) of the first dose date of study drug, and
- The AE onset date is the same as or before the month and year (or year) of the date corresponding to the cutoff day in the TEAE definition in Section 7.1.5.1.

An AE with completely missing onset and stop dates, or with the onset date missing and a stop date later than the first dosing date of any study drug, will be considered to be treatment emergent in both the Analysis for 12 Week Regimen and Analysis for 48 Week Regimen. In addition, an AE with the onset date missing and incomplete stop date with the same or later month and year (or year alone if month is not recorded) as the first dosing date of any study drug will be considered treatment emergent.

#### 7.1.6. Summaries of Adverse Events and Deaths

AEs will be summarized based on the Safety Analysis Set.

3 sets of summaries will be generated: (1) all TEAEs for 12 Week Regimen (2) all TEAEs for 48 Week Regimen (Group 1-3, and 5). (3) all AEs during TFFU period (AEs that occur during TFFU after Week 48) will be listed, and summary tables will be presented using the TFFU Analysis Set as appropriate.

A brief, high-level summary of the number and percentage of subjects who experienced at least 1 TEAE in the categories described below will be provided by treatment group. All deaths observed in the study will also be included in this summary.

The number and percentage of subjects who experienced at least 1 TEAE will be provided and summarized by SOC, PT and treatment group:

- TEAEs (with severity)

For the AE categories described below, summaries will be provided by PT and treatment group:

- TEAEs
- TEAEs of Grade 3 or higher
- TE treatment-related AEs
- GS-9992 only TE treatment-related AEs (Group 1, 3-5)
- TE treatment-related AEs of Grade 3 or higher
- TE SAEs
- TE treatment-related SAEs
- TEAEs leading to premature discontinuation of GS-9992
- TEAEs leading to premature discontinuation of TAF
- TEAEs leading to dose modification or temporary interruption of GS-9992
- TEAEs leading to dose modification or temporary interruption of TAF

Multiple events will be counted only once per subject in each summary. Adverse events will be summarized and listed first in alphabetic order by SOC and then by PT in descending order of total frequency within each SOC. For summaries by severity grade, the most severe grade will be used for those AEs that occurred more than once in an individual subject during the study.

In addition to the by-treatment summaries described above, data listings will be provided for the following AEs:

- All AEs, indicating whether the event is treatment-emergent
- All AEs of Grade 3 or higher
- SAEs
- All deaths
- AEs leading to premature discontinuation of any study drug
- AEs leading to dose modification or temporary interruption of any study drug

For subjects in the TFFU Analysis Set, by-subject listings will be provided as follows:

- All AEs
- AEs of Grade 3 or higher
- All SAEs
- All deaths

The listings will indicate whether an event is treatment-emergent, and whether the event occurred during TFFU.

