### **24 Week Treatment-Free Follow-up (TFFU)**

Subjects that meet any one of the following criteria will be followed for 24 weeks or until the initiation of alternative CHB therapy, whichever comes first:

- Subjects that discontinue all HBV therapy (eg, GS-9992 and/or TAF or commercially available NUC), for any reason;
- Subjects with HBsAg loss confirmed at least 12 weeks apart should discontinue all HBV therapy following confirmation.

The total time to complete all study visits is up to approximately 79 weeks including the following periods:

- Up to 45 day (6 to 7 weeks) screening period
- A 48-week study period

Groups 1, 3 and 5: 12 week treatment of GS-9992 plus TAF followed by TAF only treatment

Group 2: 48 weeks of TAF only treatment

Group 4: 12 week treatment of GS-9992 plus commercially available NUC followed by NUC only

- Up to 24-week TFFU period

The schedule of assessments is provided as an appendix to the SAP ([Appendix 1](#)).

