### 7.2.3.2. Laboratory Abnormalities during TFFU Period

Laboratory abnormalities during TFFU Period are defined as values that increase at least 1 toxicity grade from TFFU baseline at any post treatment time point, up to the end of the study.

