### 7.2.3.3. Summaries of Laboratory Abnormalities

Laboratory data that are categorical will be summarized using the number and percentage of subjects in the study with the given response at baseline and each scheduled postbaseline visit for treatment emergent laboratory abnormalities. Laboratory abnormalities during TFFU period will be summarized using the number and percentage of subjects in the study with the given response at TFFU baseline and each scheduled post treatment visit.

3 sets of summaries will be generated: (1) all TE laboratory abnormalities for 12 Week Regimen (2) all TE laboratory abnormalities for 48 Week Regimen for Groups 1-3, 5. (3) all laboratory abnormalities during TFFU after Week 48 for subjects in the TFFU Analysis Set will be listed, and summary tables will be presented using the TFFU Analysis Set as appropriate.

The following summaries (number and percentage of subjects) for laboratory abnormalities will be provided by lab test and by treatment group; subjects will be categorized according to the most severe postbaseline or post TFFU baseline abnormality grade for a given lab test:

- Graded laboratory abnormalities
- Grade 3 or 4 laboratory abnormalities

For all summaries of laboratory abnormalities, the denominator is the number of subjects with nonmissing postbaseline or post TFFU baseline values. A by-subject listing of Grade 3 or 4 laboratory abnormalities, and all graded laboratory abnormalities will be provided by subject ID number and visit in chronological order. This listing will include all test results that were collected throughout the study for the lab test of interest, with all applicable severity grades or abnormal flags displayed.

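### The treatment-free follow-up AE summary is limited to events after Week 48, so non-fatal SAEs in early stoppers can fall in no AE summary set; the laboratory section contradicts itself on the same limit

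*SAP*

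**What the plan says.** SAP 7.1.6 sets up three groups of AE summaries. The first two are treatment-emergent AEs for the 12-week and 48-week regimens. The third is "3) all AEs during TFFU period (AEs that occur during TFFU after Week 48) will be listed". Tabulation of this third set is promised only conditionally; the SAP's words are that "summary tables will be presented using the TFFU Analysis Set as appropriate".

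SAP 1.2 sends the following subjects into TFFU: "Subjects that discontinue all HBV therapy (eg, GS-9992 and/or TAF or commercially available NUC), for any reason". Protocol 3.2 says the same. The TFFU Analysis Set (SAP 3.1.4) and the TFFU analysis (SAP 2.1.3) cover everyone who enters TFFU, whenever that happens.

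SAP 7.1.5.1 closes the 48-week treatment-emergent window 3 days after the last TAF dose, or 30 days after the last GS-9992 dose if later, in Groups 1, 3 and 5. In Group 2 it closes 3 days after the last TAF dose. Protocol 6.5 and 7.3 collect SAEs through TFFU, and other AEs until 30 days after the last study drug.

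Two other provisions of 7.1.6 matter. On deaths: "All deaths observed in the study will also be included in this summary". On the by-subject listings for the TFFU Analysis Set, which carry no Week 48 limit: "The listings will indicate whether an event is treatment-emergent, and whether the event occurred during TFFU".

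For graded laboratory abnormalities, SAP 7.2.3.2 defines a TFFU abnormality "at any post treatment time point, up to the end of the study". The opening paragraph of 7.2.3.3 summarizes TFFU abnormalities by "number and percentage of subjects in the study with the given response at TFFU baseline and each scheduled post treatment visit". Set (3) of the same section reads "3) all laboratory abnormalities during TFFU after Week 48 for subjects in the TFFU Analysis Set will be listed". SAP 7.2.2 and 7.2.4 place no Week 48 limit on their TFFU summaries.

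**The concern.** The wording of set (3) fits a subject who completes 48 weeks and then stops. It does not fit one who stops earlier. For that subject the treatment-emergent sets close within days of the last dose, and set (3) does not open until Week 48. SAEs are still being collected in between, but no summary set takes them.

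A TFFU AE table programmed from this text would keep early stoppers in the denominator while leaving out their off-treatment SAEs before Week 48. Protocol 6.11 lists related Grade 3 or higher AEs and unacceptable toxicity among the reasons for stopping, so some of these subjects will have stopped for toxicity. On the laboratory side, two programmers could read 7.2.3.3 and produce different TFFU counts of Grade 3 or 4 abnormalities.

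**Working it through.** **Inputs.** Week 48 is nominal Day 337 (SAP Table 3-1). TFFU lasts 24 weeks, 24 × 7 = 168 days, or less if alternative therapy starts (SAP 1.2). Treatment-emergent (TE) cut-offs are from SAP 7.1.5.1. The stop days below are illustrative assumptions; the documents give no stopping rates.

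**Check on the plan's own figure.** The 12-week cut-off for Group 2 is stated as Day 114: 12 × 7 + 30 = 114. It reproduces.

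**Formulas.** Let d be the last TAF day and g the last GS-9992 day, with d at or after g.

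- TE end = max(d + 3, g + 30) in Groups 1, 3 and 5; d + 3 in Group 2. The 12-week window never ends later: it is g + 30 in Groups 1, 3 and 5. In Group 2 it is Day 114 for those still on TAF then, and otherwise at most d + 3.
- TFFU runs from d + 1 to d + 168.
- TFFU days after the cut-off = d + 168 − TE end.
- Days in no summary set = max(0, min(337, d + 168) − TE end).
- For non-serious AEs, replace d + 168 by d + 30, where routine collection ends.

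| Case | TE end | Days in no set / TFFU days after cut-off | Same, non-serious AEs (days) |
|---|---|---|---|
| g = d = 84 | 114 | 138 / 138 | 0 |
| g = 84, d = 100 | 114 | 154 / 154 | 16 |
| g = 84, d = 111 | 114 | 165 / 165 | 27 |
| Group 2, d = 84 | 87 | 165 / 165 | 27 |
| g = 84, d = 169 | 172 | 165 / 165 | 27 |
| g = 84, d = 200 | 203 | 134 / 165 (81%) | 27 |
| g = 84, d = 250 | 253 | 84 / 165 (51%) | 27 |
| g = 84, d = 300 | 303 | 34 / 165 (21%) | 27 |
| g = 84, d = 334 | 337 | 0 / 165 | 0 |

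The turning point is Day 337 − 168 = 169. Anyone who stops by then has a TFFU that ends by Week 48, so nothing from that subject can enter set (3).

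**Group 4.** This group has no 48-week TE set. With GS-9992 stopped on Day 84 and the NUC on Day 140, the only TE window ends on Day 114 and TFFU runs from Day 141 to Day 308, so all 168 TFFU days are in no set.

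**Laboratory text.** No arithmetic applies. Within 7.2.3.3, the opening paragraph covers every scheduled post-treatment visit and set (3) covers only the period after Week 48. Both cannot govern the same summary. Section 7.2.3.2 is a definition rather than a summary rule, but it also runs from the end of treatment without the limit.

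**The case against.** The strongest reply is that nothing is lost. Protocol 8.6.2 promises tables of treatment-emergent AEs only and puts all other AEs in listings. Set (3) is first a listing, with tables only where judged appropriate. The separate TFFU listings are unrestricted and flag TFFU events, and all deaths are summarized. Protocol 8.6 ends the primary safety analysis four weeks after the last GS-9992 dose, and most of the affected days lie beyond that. SAP 6.4 records that development of GS-9992 has stopped. All of this is correct and limits the consequence. It does not repair the rule: the SAP provides for TFFU tables, and any such table would undercount against its own denominator.

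On laboratory data, SAP 7.2 says summaries include all available data. The sentence in 7.2.3.3 introducing the graded tables uses the most severe grade after TFFU baseline, without a Week 48 limit. One phrase therefore stands against otherwise consistent text. That points to which reading was intended, but the contradiction remains until the phrase is removed.

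Day 337 comes from a visit-window table, not from the AE section. The AE section counts 12 weeks as Days 1 to 84, which would put the end of 48 weeks at 48 × 7 = Day 336. On that count the partial figures fall by one day (133, 83 and 33), the Day 169 case becomes 164 of 165, and the gap closes from Day 333. The conclusion does not change.

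It may be that the phrase was only a loose label for TFFU. The SAP does not say so, and if it was, deleting it changes nothing.

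**Conclusion.** The concern holds. As written, a non-fatal SAE of a subject who stops all therapy early can fall after the treatment-emergent cut-off and before Week 48, and so enter no AE summary set. The exposed period is the whole post-cut-off TFFU for stops by Day 169 and shrinks to nothing at Day 334. Non-serious AEs are exposed for at most 27 days. For graded laboratory abnormalities the finding is a contradiction in 7.2.3.3, not an established omission.

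The day counts assume a full 168-day TFFU, Week 48 at Day 337, and TAF stopped no earlier than GS-9992. How many subjects are affected cannot be derived from the documents. The tables are descriptive and the listings are complete, so this is a reporting defect that should be fixed, not a threat to the study's conclusions.

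**What to change.** Delete the words limiting the summaries to after Week 48 in SAP 7.1.6 and in set (3) of SAP 7.2.3.3. State that the TFFU summaries count all AEs with onset after the subject stopped all HBV therapy, and all laboratory abnormalities as defined in 7.2.3.2, through the end of TFFU. The start point is the stop of TAF in Groups 1-3 and 5 and of the NUC in Group 4, as in 3.1.4; if GS-9992 stops last, its date governs. The number of TFFU days in no set is then zero for every stop day.

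Do not add a treatment-emergent cut-off to the TFFU condition, since that would drop early off-treatment events from the TFFU table. Add a footnote that events between the last dose and the treatment-emergent cut-off may appear in both tables. That overlap is TE end − d: 3 to 30 days in Groups 1, 3 and 5, and 3 days in Group 2. In Group 4 it is at most 30 days, and none if the NUC stops 30 or more days after GS-9992.

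The cost is two wording edits, one footnote and one date condition in the TFFU programs. No new data are needed. TFFU counts may rise slightly.

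One related gap is not closed by this change. In Group 4 subjects who stay on their NUC, SAEs from 30 days after the last GS-9992 dose to Week 48 are in no set, because 7.1.5.1 excludes that group from the 48-week analysis.
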